#### D. UCIMC Supplementary Clinical Services

If a UCIMC clinical unit/department (e.g., phlebotomy for blood draws, pharmacy for dispensing study drug(s), radiation services for X-rays, MRIs, CT scans, and Neurology for lumbar punctures) will perform research-related procedures:

1. List the research procedure (e.g. lumbar puncture, MRI, CT Scan), and

2. Identify the unit/department that will perform the procedure.

[] Not applicable: This study does not involve the services of a UCIMC clinical unit/department.

Treatment for vitiligo will occur at UCI Department of Dermatology.

[name] and his staff will perform the melanocyte-keratinocyte transplant procedure and follow-up evaluations.

#### E. Privacy

Privacy is about the subject's ability to control how much others see, touch, or collect information about the subject. Indicate all of the following methods that will be used to assure subject privacy. *Violations of privacy include accessing a subject's private information without consent, asking personal sensitive information in a public setting, being audio recorded or photographed without consent.* 

**[ x ]** Research procedures (including recruitment) are conducted in a private room.

**[ x ]** Use of drapes or other barriers for subjects who are required to disrobe.

[x] Only sensitive information directly related to the research is collected about subjects.

[ ] When information is collected from internet sources, the internet site's privacy statement will be reviewed and followed.

Provide a copy of the Data Use Policy to the IRB.

[ ] Other (specify): <Type here>

#### F. Use of Existing Biological Specimens and/or Existing Information/Data

- 1. For studies that involve use of existing (i.e. on the shelf; currently available) specimens:
  - a. Indicate the source of the specimens and whether the specimens were originally collected for research purposes.
  - b. Explain how the existing specimens will be obtained.

x ] Not applicable: This study does not involve use of existing biological specimens.	
Source: Indicate all that apply: ] UCI/UCIMC Driginally collected for research purposes: []YES; UCI IRB number (i.e. HS#): <type here=""> []NO; explain: <type here=""></type></type>	
] UCIMC Pathology Biorepository will provide specimens.	
] Non-UCI Entity; specify: <type here=""> Driginally collected for research purposes: []YES Submit a copy of the IRB Approval Notice and Consent Form for the original collection. []NO; explain: <type here=""></type></type>	
[ ] Other; explain: <type here=""></type>	

 
For studies that involve use of existing (i.e. on the shelf; currently available) clinical data:
 
a. Specify the source of the clinical data.
 
	

b. Explain how the study team will access the clinical data. Access to UCI Medical Center medical records for research purposes outside the capacity of the Honest Broker Services, such as access to physician notes, must be obtained from the Health Information Management Services.

*For investigator initiated/authored studies only, submit a data abstraction sheet that includes a complete list of data elements/information that will be collected from (existing) records or submit the case report form (CRF; eCRF).* 

[] Not applicable: This study does not involve use of existing clinical data. Skip to Section 6.G.

#### Source: Indicate all that apply:

**[ x ]** UCI/UCIMC.

[ ] non-UCI Entity; specify: <Type here>

#### How Obtained: Indicate all that apply:

- [ ] The study team will request specific patient information/data from UCIMC Health Information Management Services.
- [ x] The study team will review their patients' records and abstract data directly from those records.
- [ ] The study team will request specific patient information/data from UCI Health Honest Broker Services. Describe the following:

Cohort selection criteria (e.g., use the available Clinical Terms from the Cohort Discovery Tool such as Demographics: Gender, Diagnoses: Asthma, Procedures: Operations on digestive system): <Type here>

Expected cohort size/patient count: <Type here>

Cohort attributes or data elements (e.g., lab test values, medication, etc.): <Type here>

- [ ] Other; explain: <Type here>
- 3. For studies that involve use of existing (i.e. on the shelf; currently available) clinical data, specify the time frame of the clinical data to be accessed (e.g. records from January 2002 to initial IRB approval).

The duration of the study.

#### G. Collection of Photographs, or Audio/Video Recording

- 1. Describe all procedures involving the use and/or collection of photographs, or audio/video recording.
- [] Not applicable: This study does not involve photographs or audio/video recording. *Skip to Section 6.H.*
- 2. Specify if photographs or audio/video recording will include subject identifiable information (e.g., name, facial image). If so, indicate which identifiers will be collected.

No photographs will be taken that include subject identifiers. The areas taken will include the donor site and recipient site of the graft at each clinical visit (1 day, 4 days, 1 month, 3 months, and 6 months).

3. Explain whether the photographs or audio/video recording will be included in subsequent presentations and/or publications and, if so, whether subject identifiers will be included.

No presentation or publications from this research will include photographs that will include subject identifiers.

#### H. Sharing Results with Subjects

- 1. Describe whether individual results (results of investigational diagnostic tests, genetic tests, or incidental findings) will be shared with subject or others (e.g., the subject's primary care physician). Only tests ordered by a physician and conducted in a CLIA certified lab may be shared.
- 2. Explain what information will be shared and how the results will be shared.

[x] Not applicable: Individual results will not be shared with subjects.

<Type here>

- 3. Describe whether overall study results will be shared with subjects.
- 4. Explain how results will be shared.

[x] Not applicable: Final study results will not be shared with subjects.

<Type here>

#### I. Statistical Considerations (This section is required for Investigator-Authored Research)

1. Statistical Analysis Plan: Describe the statistical method(s) for the stated specific aims and hypotheses. Your analysis plans should match the stated study specific aims and hypotheses in Section 1.

[] Not applicable

This is an observational study to examine response to therapy using change in surface area and VES score. There will be no measurement other than improvement in surface area and VES score as a measure of improvement before and after the procedure.

2. Describe the primary statistical method(s) that will be used to analyze the primary outcome(s) or endpoints.

We will measure the VES score and surface area change in the transplanted area before and after the procedure. The rate of change in surface area and VES will be measured as an outcome measure. This study is powered to examine if the initial procedure induces significant repigmentation (10 patients for each arm) and is also sufficient to compare the initial procedure to the procedure with the blister grafting technique.

3. Describe the secondary statistical method(s) that will be used to analyze the secondary outcome(s) or endpoints.

N/A

4. If appropriate describe secondary or post hoc analyses of primary outcome(s) or other exploratory analysis.

N/A

5. Sample Size Determination: Explain how the overall target sample size was determined (e.g., power analysis; precision estimation), providing justification of the effect size for the primary outcome based on preliminary data, current knowledge/literature and/or cost consideration; if appropriate, provide sample size justification for secondary outcomes. Power analysis should (at least) match the primary outcome/endpoint.

With a sample size of 5 patients in each arm, this study will achieve 90% power to test the hypothesis for each arm based on a two-sided paired t-test at p=0.05 significance level.

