On the second arm of the study, we are using a minimally invasive procedure (suction blister grafting) to sample the grafted skin and donor skin- this method can separate the epidermis from the dermis without inducing a scar. A normally pigmented area on the upper thigh is anesthetized with 1% lidocaine with epinephrine. Using a suction blister technique, we remove a small portion of the epidermis that is unaffected by vitiligo from a small area (4 cm^2 or 0.6 inch) on the patient's thigh to obtain donor cells. Epidermis that was harvested is washed with Lactated Ringers solution three times, and then dissociated using trypsin to separate the cells into a single cell suspension. The recipient areas to be grafted is used to harvest epidermis using a suction blister device. Half of the dissociated single cells from the donor area (thigh) are then transplanted on to the area affected by vitiligo that the patient was interested in grafting (5 cm^2 area or 0.7 inch). The suction blister skin from the recipient sites is simultaneously dissociated into a single cell suspension. A portion of the remainder of the cells (from both the donor and recipient site) is subjected to flow sorting to quantify the populations of melanocytes and keratinocytes. Another portion of the remainder cells are submitted for single cell RNA-sequencing at the genomics and high throughput facility to identify the spectrum of different types of melanocytes and keratinocytes in the epidermis using single cell RNA-sequencing technology. We then evaluated response to treatment in the transplanted areas at 1 day, 1 week, 1 month and 3 months, and 6 months by both photography and quantifying the VASI score. This arm of the study is nearly complete, with only 2-3 more patients to enroll to complete the statistical evaluation of efficacy.

VASI is the percentage of vitiligo involvement and is calculated in terms of hand units. One hand unit is approximately equivalent to 1% of the total body surface area.

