3. Describe the purpose, specific aims or objectives. Specify the hypotheses or research questions to be studied.

The purpose of this study is to compare the result of suction blister grafting without cell dissociation versus suction blister grafting with cell dissociation and MKTP with blade technique and determine whether cellular dissociation impacts the outcome. In the first arm of this study, seven patients were enrolled, and the procedure was done successfully without complication. Follow up was accomplished and outcomes will be analyzed at the end of the study. In the second arm of the study, we have conducted the MKTP with suction blistering in 7 patients and then will compare the results with previous study. In the third arm of the study, we are planning to perform suction blister grafting without epidermal cell dissociation on a total of seven patients. We want to evaluate the importance of cell dissociation on the outcome of this procedure.

This information and experience will be important worldwide for the vitiligo community, as it is the only study that compares the efficacy of these three methods in a single study. This will help us better advice and counsel patients on the best procedure for them when we discuss the options. UCI is the only center on the west coast offering this procedure, so ensuring the efficacy of the methods is important.

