#### SECTION 3: SUBJECT POPULATION(S) (INDIVIDUALS/RECORDS/SPECIMENS)

#### A. Subjects To Be Enrolled on this UCI protocol (Persons/Records/Biospecimens)

- 1. Complete the table of subject enrollments below. *Include additional rows for subject category/group, as needed.*
- 2. If the study involves the use of existing records or biological specimens, specify the maximum number to be reviewed/collected and the number needed to address the research question.

Category/Group (e.g., adults, controls, parents, children)	Age Range (e.g., 7-12, 13–17, adults)	Maximum Number to be Consented or Reviewed/Collected (include withdrawals and screen failures)	Number Expected to Complete the Study or Needed to Address the Research Question
1-First Arm-Harvesting with surgical Blade(adults)	18 years and older	10	7 completed
2- Second Arm-Suction Blistering Method (adults)	18 years and older	10	7
3-Third Arm-Suction Blister grafting without cell dissociation	18 years and older	10	7
		Total: 30	

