#### Study Endpoints:

We hypothesize that our transplant procedure will yield excellent to good repigmentation, resulting in a mean of 60% reduction in surface area and VASI scores (SD=30%) from baseline to 6-month follow up. With a sample size of 5 patients, this study will achieve 90% power to test this hypothesis based on a two-sided paired t-test at p=0.05 significance level. This will be measured by both the physician and captured via digital photography. In the second arm of the study, we will compare the results with skin harvested with a blade as compared to a suction blister method. In the third arm of the study, we will compare the results skin harvested with a blade as compared to a suction blister method as used to a suction blister with dissociation and suction blister without dissociation.

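### Section 6.I gives two conflicting powered sizes for the within-arm test, 10 and 5 per arm, and neither is the 7 per arm that the trial plans

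*Combined protocol and SAP*

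**What the plan says.** Three different numbers per arm appear.

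- **Ten.** Section 6.I item 2 (primary statistical method): "This study is powered to examine if the initial procedure induces significant repigmentation (10 patients for each arm". It attaches no mean, SD, test or power to the 10. The sentence goes on to claim that the size is also enough to compare the initial procedure with the blister technique.
- **Five.** Section 6.I item 5 (sample size determination): "With a sample size of 5 patients in each arm, this study will achieve 90% power to test the hypothesis for each arm". The test named there is a paired t-test, two-sided, at the 5% level. The effect assumed is in Section 6.B item 2, Study Endpoints: "resulting in a mean of 60% reduction in surface area and VASI scores (SD=30%) from baseline to 6-month follow up". The Non-Technical Summary, Section 1 item 4 and Study Endpoints also give 5 with 90% power.
- **Seven.** The table in Section 3.A lists 7 per arm as the number expected to complete or needed. It lists 10 per arm in the column headed "Maximum Number to be Consented or Reviewed/Collected (include withdrawals and screen failures". Section 1 item 3 gives seven for each arm; for the third, "we are planning to perform suction blister grafting without epidermal cell dissociation on a total of seven patients". The Non-Technical Summary also compares groups of seven.

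The second arm's status is described in two ways. The Non-Technical Summary has it nearly complete, "with only 2-3 more patients to enroll to complete the statistical evaluation of efficacy"; Section 1 item 3 says "we have conducted the MKTP with suction blistering in 7 patients".

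**The concern.** Items 2 and 5 answer the same question, whether the procedure produces significant repigmentation within an arm, with sizes that differ by a factor of two. Neither is the number being treated, and no power statement is attached to 7. A reader cannot tell which number the trial rests on, or what power the planned arms have. Because 10 appears in Section 3.A only as a ceiling that counts withdrawals and screen failures, item 2 credits the trial with more evaluable patients than it expects.

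**Working it through.** **Inputs.** Mean reduction 60% and SD 30% (Study Endpoints); two-sided paired t-test at 0.05 (Section 6.I item 5); n = 5 (item 5), 7 (Section 3.A) and 10 (item 2). Item 2 states no effect, so using 60 and 30 at n = 10 is my assumption.

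**Formula.** Standardised effect d = 60/30 = 2.0; degrees of freedom n − 1; noncentrality d√n. Power is the probability that a noncentral t exceeds the two-sided 5% critical value in absolute size.

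**The plan's own figure.** At n = 5, noncentrality = 2√5 = 4.47 on 4 degrees of freedom, and power = 0.909. The stated 90% reproduces. At n = 4 power is 0.755, so 5 is the smallest number that reaches 90%.

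**The same test at each size.** The fourth column is the d that gives 90% power. The fifth is that d × 30, and the sixth is 60 divided by it.

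| n per arm | Noncentrality | Power (mean 60, SD 30) | d for 90% power | Mean detectable at SD 30 | Largest SD at mean 60 |
|---|---|---|---|---|---|
| 5 | 4.47 | 90.9% | 1.966 | 59.0 | 30.5 |
| 7 | 5.29 | 99.1% | 1.479 | 44.4 | 40.6 |
| 10 | 6.32 | 99.98% | 1.155 | 34.6 | 52.0 |

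With 7 completers the within-arm test has more power than item 5 claims. Two of the seven could be lost and the stated 90% would still hold.

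**The clause attached to item 2's number.** Correcting 10 to 7 would make the sentence say that 7 per arm suffices to compare techniques. The plan gives no difference, SD, test or power for that comparison. I assume a two-sample t-test, SD 30 points in each arm and two-sided 0.05 without adjustment. The noncentrality is then D / (30√(2/n)).

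| True difference D (points) | Power, 7 v 7 | Power, 10 v 10 |
|---|---|---|
| 10 | 8% | 11% |
| 20 | 21% | 29% |
| 30 | 41% | 56% |
| 40 | 63% | 81% |

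The difference detectable with 80% power is about 49 points at 7 per arm and about 40 at 10 per arm.

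**The case against.** The strongest defence is that the numbers form a sensible ladder: 5 is the minimum for 90% power, 7 are expected to complete, and up to 10 may be consented. On that reading only the parenthesis in item 2 is out of place, and nothing about the conduct of the trial or its within-arm conclusion changes. Most of this stands. It is why the point is about a misstated size and not about an underpowered test. It does not rescue item 2, which calls 10 powered in the section where item 5 says 5.

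A reader might infer more, and the documents do not support it:

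- *That the test is sized three ways, or that all three sizes are called sufficient.* Only 5 and 10 are described as powered. Seven is the number expected or needed, with no power attached.
- *That item 2 took its 10 from the consent ceiling.* The figures match, but no text makes the link.
- *That an arm could be tested repeatedly and closed at a favourable size, inflating the type I error.* No interim test is described. Section 1 item 3 says the first arm's outcomes will be analysed at the end of the study, and Section 1 item 4 places the comparison after all three arms. The first arm is already fixed at 7 completed.
- *That the second arm may end at 9 or 10.* The Non-Technical Summary describes its seven patients as almost completed, and Section 3.A gives 7. The two or three still to enrol read naturally as part of the seven, so what remains is a conflict in status wording with Section 1 item 3.

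**Conclusion.** The point holds as an inconsistency in the stated sample size. Section 6.I gives 10 and 5 for one question, the trial plans 7, and 10 is a size that the enrolment table does not expect any arm to reach. The 90% at n = 5 is correct (0.909). On the same inputs the planned 7 gives 99.1%, so the plan understates its within-arm power. These figures rest on the plan's 60% and 30%, and on treating percentage change as roughly normal in very small samples.

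The practical risk lies in how the correction is made. If 7 simply replaces 10, the unsupported claim of sufficiency for comparing techniques passes to the smaller number. Under an assumed SD of 30 points per arm, only very large differences between techniques are detectable at that size.

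**What to change.** 1. In Section 6.I item 2, replace the parenthesis with: '7 evaluable patients per arm; up to 10 consented'.
2. In the same sentence, delete the claim that the size suffices to compare techniques, or call that comparison exploratory.
3. In Section 6.I item 5, and where the figure recurs (Non-Technical Summary, Section 1 item 4, Section 6.B item 2), state that with 7 per arm the two-sided paired t-test at 0.05 has about 99% power for a mean of 60% (SD 30%). Equivalently, it has 90% power for a mean of about 44% (SD 30%), or for an SD up to about 40% (mean 60%). Add that 5 is the smallest number giving 90%.
4. Make the second arm's status agree between the Non-Technical Summary and Section 1 item 3, with 7 as the target.

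The cost is wording only. No patients, visits or measurements are added. The sponsor gives up the claim of 10 powered patients per arm and the unsupported claim about comparing techniques.

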On the now proposed third arm of the study, we use a minimally invasive procedure (suction blister grafting without cell dissociation) to sample the grafted skin and donor skin- this method can separate the epidermis from the dermis without inducing a scar. A normally pigmented area on the upper thigh will be anesthetized with 1% lidocaine with epinephrine. Using an epidermal harvesting system which is a suction blister technique, we will remove multiple small portions (about 128 blisters-1.8 mm in diameter) of the epidermis unaffected by vitiligo from a small normal area (5 cm^2) on the patient's thigh to obtain donor cells and using a regular negative pressure instrument for removing four samples for histopathological study (two from the vitiligo area and two from the normal donor skin). The epidermis from the donor area (thigh) will then be transplanted on to the area affected by vitiligo that the patient is interested in grafting. Also, the four portions from the normal skin and the recipient site will be sent for the histopathological evaluation.

We will then evaluate response to treatment in the transplanted areas at 1 day, 1 week, 1 month and 3 months, and 6 months by both photography, quantifying the change in depigmented surface area, and the VASI score. Also, we will evaluate the two vitiligo samples and two normal skin samples through histopathology to assess where the unique populations of cells identified in our RNA-seq analysis are localized. We hypothesize that our transplant procedure will yield excellent to good repigmentation, resulting in a mean of 60% reduction in surface area (SD=30%) from baseline to 6-month follow up. With a sample size of 5 patients, this study will achieve 90% power to test this hypothesis based on a two-sided paired t-test at p=0.05 significance level. In addition, we will compare the results from the 7 patients harvested using the surgical blade technique (procedure already completed and follow up results pending) with the results from 7 patients harvested with the suction blisters (almost completed) and seven patients from the newly proposed experimental group.

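### Section 6.I.2 calls the sample sufficient to compare two procedures, but no between-arm calculation exists; at SD 30 and 80% power the detectable difference is about 40 points at 10 per arm and 49 at 7 (assumed settings)

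*Combined protocol and SAP*

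**What the plan says.** Section 6.I, item 2 first says the study is powered, with 10 patients in each arm, to show that the initial procedure repigments skin. It then adds that the study "is also sufficient to compare the initial procedure to the procedure with the blister grafting technique". The natural reading is arm 1 (surgical blade) against arm 2 (suction blister with dissociation). The outcome is described there as follows: "The rate of change in surface area and VES will be measured as an outcome measure".

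The sample size justification in item 5 covers only the change within an arm: "With a sample size of 5 patients in each arm, this study will achieve 90% power to test the hypothesis for each arm", by a two-sided paired t-test at 0.05. The inputs are in Section 6.B, item 2: "mean of 60% reduction in surface area and VASI scores (SD=30%) from baseline to 6-month follow up". The Non-Technical Summary and Section 1, item 4 repeat the calculation. Item 3 of Section 6.I (secondary methods) is answered N/A. So is item 4, which asks the author to "describe secondary or post hoc analyses of primary outcome(s) or other exploratory analysis".

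The number of patients per arm varies:

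- In the enrolment table of Section 3.A, 10 stands in the column headed "Maximum Number to be Consented or Reviewed/Collected (include withdrawals and screen failures". The next column, for the number expected to complete or needed, gives 7 for each arm, and arm 1 is marked as completed.
- The Non-Technical Summary says "we will compare the results from the 7 patients harvested using the surgical blade technique" with 7 in each of the other two arms.
- Section 1, item 3 says "In the second arm of the study, we have conducted the MKTP with suction blistering in 7 patients".

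**The concern.** Section 1, item 3 makes comparison of the techniques the purpose of the study and says the results should help in advising patients which procedure to choose. An assurance that the sample suffices for that comparison therefore matters, and it has no calculation behind it. A within-arm calculation cannot supply one. It tests a mean change of 60 points against zero, whereas the comparison tests a difference between two such changes, which is presumably much smaller and carries sampling error from both arms.

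An imprecise comparison is acceptable in a pilot. The harm comes from calling it sufficient, because a non-significant result could then be taken to mean that the techniques perform alike when the data could not show that.

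**Working it through.** **1. The plan's own figure.** Paired t-test, two-sided 0.05, standardised effect 60/30 = 2. With n = 5, df = 4 and noncentrality 2 × √5 = 4.47, the noncentral t gives power 0.909. The stated 90% reproduces, and n = 4 gives only 0.755. Power is 0.991 at n = 7 and 0.9998 at n = 10. The within-arm claim is sound.

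**2. Which n applies.** Seven per arm are expected to complete and are the patients to be compared. Arm 1 is finished at 7, so 10 v 10 is not available for this comparison unless arm 1 reopens. The most favourable case otherwise is 7 v 10, which needs every patient of arm 2's consent maximum to complete.

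**3. Detectable difference.** The inputs are:

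- SD 30 points, from Section 6.B, item 2. Its use as a common SD in both arms is my assumption.
- Two-sided 0.05, carried over from the paired test (assumption).
- 80% power (assumption; the plan's only power level is the within-arm 90%).
- Endpoint: percent reduction from baseline to 6 months, the only measure with a stated SD. None is given for the rate of change or the VES score named in item 2, so sufficiency on those cannot be checked.

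SE = 30 × √(1/n₁ + 1/n₂). The 95% CI half-width is t(0.975; n₁+n₂−2) × SE. The detectable difference D solves power = 0.80 for a noncentral t with noncentrality D/SE.

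| n per arm | SE | t | CI half-width | D at 80% power |
|---|---|---|---|---|
| 10 v 10 | 13.42 | 2.101 | 28.2 | 39.7 |
| 7 v 10 | 14.78 | 2.131 | 31.5 | 44.3 |
| 7 v 7 | 16.04 | 2.179 | 34.9 | 49.0 |
| 5 v 5 | 18.97 | 2.306 | 43.8 | 60.7 |

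At 90% power, D is 56.7 points at 7 v 7 and 46.0 at 10 v 10. The whole expected effect of a procedure is 60 points.

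**4. If the SD is smaller.** D scales with the SD. At 7 v 7 it is 48.95 × 20/30 = 32.6 points for SD 20, and 48.95 × 15/30 = 24.5 for SD 15.

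**5. Power for moderate differences.** The documents state no target, so these are illustrations. At SD 30, a true 20-point difference has 21% power at 7 v 7 and 29% at 10 v 10; a 30-point difference has 41% and 56%. At 7 v 7, 20 points has 41% power if the SD is 20 and 63% if it is 15.

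**6. Bounded scale.** Percent reduction cannot exceed 100, and the SD may shrink near either end. This was checked by simulation at 7 v 7 (beta-distributed reductions on 0–100, pooled t-test), with the bounds and SDs as assumptions. One arm has mean 60 and SD 30, except in the last row.

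| Other arm's mean (SD) | Power |
|---|---|
| 80 (15–30) | 25–27% |
| 90 (10–20) | 55–63% |
| 95 (5–10) | 79–84% |
| 20 (10–15) | 79–84% |
| 40 v 80 (SD 20 in each arm) | 89% |

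Reliable detection needs near-complete repigmentation against 60%, a technique that largely fails, or a gap of about 40 points with a smaller spread.

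**The case against.** **The sentence reserves its power language for the within-arm test and says only that the sample suffices to compare, in a study that calls itself a pilot.** A purely descriptive meaning is conceivable. But the clause completes a sentence that opens as a statement of power, it stands under primary statistical methods, and comparison is the stated purpose. If only description is meant, the plan should say so.

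**The sentence uses 10 per arm, so 49 points judges it at another n.** It is fair to report both. At 10 v 10 the figure is about 40 points, and the conclusion is unchanged. Arm 2's final number is also not quite settled: the Non-Technical Summary speaks of two or three patients still to enrol, while Section 1 reports 7 treated. The range from 7 v 7 to 7 v 10 covers this.

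**The 80% power and the common SD are the reviewer's.** That stands, and the result is conditional on them. The plan's own 90% makes it worse. An SD of 15 halves the detectable difference but still leaves 24.5 points.

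**Stronger readings that do not hold.** From the 100% ceiling, a reader might infer that a difference can be detected only if the better arm averages about 95%. That covers one direction only. The other arm may be the worse one, and 20% against 60% is detected about as often; so is 40% against 80% at SD 20. Nor does the finding show that the sample size calculation is wrong: n = 5 is right for the test it describes. No passage plans to conclude equivalence either, so misreading a null result is a risk and not something the sponsor has announced.

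**Conclusion.** The statement that the sample suffices to compare the two procedures is unsupported and should not stand. Nothing in the documents defines what the comparison should detect. On the plan's own SD, the detectable difference is about 40 points at the n in the sentence and about 49 at the n expected, with an interval of about ±35 points at 7 per arm. These figures rest on percent reduction as the endpoint, a common SD of 30, a two-sided 0.05 level and 80% power. They apply to a single comparison; a Bonferroni correction for three pairwise tests would raise 49 to about 59.

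The within-arm objective is unaffected. The absence of any described randomisation, the differing preparation of recipient sites, and the use of both VASI and VES as names for the score are separate points and add nothing to this one.

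**What to change.** 1. **Section 6.I, item 2.** Delete the clause "is also sufficient to compare the initial procedure to the procedure with the blister grafting technique" with its connecting words. Replace the 10 per arm with the 7 patients expected to complete in each arm, for whom within-arm power is about 99% at mean 60 and SD 30.
2. **Section 6.I, item 5, the Non-Technical Summary, Section 1, item 4 and Section 6.B, item 2.** Keep the 5 but label it as the minimum number for 90% within-arm power. The 5, 7 and 10 then have distinct meanings.
3. **Section 6.I, item 4.** Replace N/A with text such as: *Between-arm comparisons of percent reduction from baseline to 6 months are exploratory, unadjusted for multiplicity, and reported as differences in means with 95% confidence intervals (expected half-width about 35 points at 7 per arm if the SD is 30). A non-significant difference will not be read as equivalence.*
4. **Section 1, item 3.** Mark the comparison of techniques as exploratory, so that aims and analysis agree as item 1 of Section 6.I requires.

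If the sponsor prefers to keep a claim of sufficiency, it must state the difference, SD, test, level and power behind it. At SD 30 and 80% power, 30 points would need 17 per arm and 20 points 37 per arm.

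The recommended change costs wording only: no extra patients, visits or procedures. The price is a more modest statement of the between-arm aim.
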